The primary study objective of this project is to investigate the effectiveness of a support group intervention using a solution-focused approach in reducing bullying, enhancing mental health, improving quality of life, and increasing general self-efficacy among school children in 5th-7th grade.

We hypothesize that the awareness of bullying created by the intervention, and the empowerment of children as contributors to the solution, will generate positive ripple effects benefiting all children in intervention schools. Furthermore, we hypothesize that children with a peer support group will exhibit lower levels of bullying, improved mental health, better quality of life, and increased general self-efficacy after the intervention compared to their baseline levels. We expect these effects to persist even after 6 and 9 months.

Aligned with the cluster RCT we will undertake a parallel process evaluation to assess the extent of the intervention coverage, whether the intervention was implemented according to the protocol and identify factors that hinder or aid the implementation of a support group intervention. For the process evaluation we will use the framework presented by the Medical Research Council guidelines focusing on the implementation (what is implemented and how), the mechanisms of impact (how does the delivered intervention produce change), and the context (how does the context affect implementation and outcomes)(Moore et al., 2015). The outline of the process evaluation is described later in the protocol.

Research questions: (prefix of p indicates primary research questions, prefix of s indicates secondary research questions)

pRQ1: To what extent do children in intervention schools report a reduction in **bullying** following a peer support group intervention compared to children in control schools receiving usual care, at intervention end and after 6- and 9 months?

pRQ2: To what extent do children in intervention schools report higher **quality of life** following a peer support group intervention compared to children in control schools receiving usual care, at intervention end and after 6- and 9 months?

pRQ3: To what extent do children in intervention schools report improved **classroom environment** following a peer support group intervention compared to children in control schools receiving usual care, at intervention end and after 6- and 9 months?

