pRQ4: To what extent do children with a peer support group report a reduction in **bullying** at the end of the intervention compared to their pre-intervention baseline level?

sRQ5: To what extent do children with a peer support group report improved **mental health** at intervention end compared to their pre-intervention baseline level?

sRQ6: To what extent do children with a peer support group report better **quality of life** at intervention end compared to their pre-intervention baseline level?

sRQ7: To what extent do children with a peer support group report increased **general self-efficacy** at intervention end compared to their pre-intervention baseline-level?

sRQ8: To what extent does the effects as measured in R1-R7 persist 6- and 9 months after intervention end compared with pre-intervention baseline level?

sRQ9: To explore the recruitment rate and factors associated with non-participation, on school, provider, and child level.

sRQ10: To describe whether the intervention was delivered according to protocol in terms of quality, quantity, adaptions and variations across schools and time.

[figure not shown]
sRQ11: To describe the intervention acceptability from children's, teachers, school nurses and residents' perspectives.

sRQ12: To investigate barriers and facilitators to intervention delivery and the mechanisms of impact.

Study design

This is a cluster randomized trial of children in 5th to 7th grade in Norwegian primary schools with randomization at school level. The cluster design is well-suited due to the significant risk of contamination between the groups with a regular RCT design. The study flow is presented in figure 1. Intervention schools will implement the SFA-model for reducing bullying, whereas the control schools will offer usual care according to national guidelines. The intervention is at two levels; (i) training of school nurses and school staff and raising awareness about the SFA-model among parents and students; for this part the outcomes will be measured at cluster-level, and (ii) implementing the SFA-model on individual participant level; for this part the outcomes will be measured on individual level in the intervention cluster only. The recruitment process, the intervention and the outcomes measured are described below.

Figure 1 Study flow for the Cluster randomized controlled trial

Methods

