The target population for the study are all school children in 5th-7th grade in primary schools in Asker, Moss and Lillestrøm municipalities in the central-eastern part of Norway. Primary schools with more than 200 students and with a school nurse appointed in at least 50% position are eligible for the study. Eligibility for having a support group established is based on the subjective experience of loneliness by the individual child and is defined as a negative emotional state caused by the discrepancy between the desired and actual social relationships, in line with Peplau et al (1).

Clusters and randomization procedure Since decisions about bullying interventions are typically made at the municipal level, we will begin the recruitment process of schools through enrolment of selected municipalities, as illustrated in figure 2. In selected municipalities consenting to participate, we will randomly invite 26 primary schools from the pool of eligible primary schools in these municipalities.

Figure 2. Illustration of the recruitment process of primary schools in xx, xxx and xxx municipalities in Norway

We will continue enrollment until the pre-identified number of schools is reached. The enrolled schools will be sorted by size and then block-randomized in a 1:1 ratio to either the intervention arm (hereafter referred to as intervention schools) or the control arm (hereafter referred to as control schools). A statistician not involved in the study will carry out the randomization procedure. After randomization, the schools will be informed about their assigned cluster and will receive more detailed information accordingly.

Sample size calculation *School level*: Based on the available literature, we anticipate that 6-10% of children in 5th -7th grade will report bullying (Krusell et al., 2019; Wendelborg, 2021). This proportion is expected to be reduced to at least 6 % in intervention schools' post-intervention. With a significance level at 5% and power at 80%, we will need 721 children in each arm. Accounting for additional variation, we would need 793 in each arm. We assume there will be three classes in each school with about 30 children in each class. Thus, we aim to include 26 schools (13 for each arm) to ensure that the study is sufficiently powered.

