Individual child level: The quality-of-life inventory KIDscreen-27 (28) has 5 domains and is scored from 0-100. For the domain "social support and peers", we anticipate a change of at least 3 points from baseline to 9 months (35). Further, when assuming a correlation of 0.7 to account for statistical dependencies (as the same child is assessed several times), and keeping significance level to 5%, we would need 55 children experiencing loneliness. To account for possible dropouts, we add additional 10% participants, i.e., 60 children.

Study procedure Essential information about the intervention, including the recruitment process and the continuation and follow-up phases will be shared with the municipality, students, parents, teachers and school nurses involved in the project. Written information about the option for support groups for children encountering challenges related to bullying at school will also be provided to parents. **Training Intervention Schools**: A group of two to three teachers or school nurses will participate in a three-day training program centered around the solution-focused approach and the support group model. This training will be led by *Adults for Children*, an organization possessing extensive expertise in implementing interventions within school settings. Following the training, the peer support group intervention will be initiated as soon as possible. **Control Schools**: In the control schools, preventive and health promotion services will be provided as usual and according to the guidelines set forth by the Norwegian Directorate of Health (29).

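### pRQ4 is labelled a primary effectiveness question, but it is an uncontrolled before-after comparison in children selected for a current adverse state, and no stated sample size supports it

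*Protocol*

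**What the plan says.** Under Study objectives the protocol opens with effectiveness: "The primary study objective of this project is to investigate the effectiveness of a support group intervention". The list of research questions then fixes the labels: "prefix of p indicates primary research questions, prefix of s indicates secondary research questions".

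pRQ1 to pRQ3 set children in intervention schools against children in control schools. pRQ4 concerns only children with a support group and asks about their reduction in bullying "at the end of the intervention compared to their pre-intervention baseline level". The Study design section describes two levels of intervention and says of the individual level: "for this part the outcomes will be measured on individual level in the intervention cluster only".

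On who these children are, the Methods section says: "Eligibility for having a support group established is based on the subjective experience of loneliness by the individual child". The Study procedure section describes the same children as experiencing bullying.

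sRQ5 to sRQ7 put the same kind of question to the same children at the same time point but are labelled secondary, for example "sRQ6: To what extent do children with a peer support group report better" quality of life. sRQ8 asks whether the results of R1 to R7, which it calls effects, last to 6 and 9 months relative to baseline.

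The individual-level sample size is 55 children, raised to 60 for dropout. It rests on a 3-point change in one KIDSCREEN-27 domain between baseline and 9 months.

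**The concern.** A before-after change in a group chosen because its members are currently doing badly mixes three things: any effect of the support group, recovery that would have happened anyway, and regression to the mean. Without a comparable untreated group they cannot be separated. pRQ4 has no such group, and no analysis can supply one from data collected only in intervention schools.

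The label is what makes this matter. As written, a fall in bullying under pRQ4 would be a primary effectiveness result of a cluster-randomised trial, although randomisation plays no part in that comparison. The follow-up in sRQ8 would carry the same reading to 6 and 9 months. A primary question would also normally have a sample size behind it, and none is stated for this one.

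**Working it through.** **1. The questions side by side** (Research questions; Table 2)

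| Question | Label | Children | Comparator | Measure |
|---|---|---|---|---|
| pRQ1–pRQ3 | primary | all students, 5th–7th grade | control schools | student survey |
| pRQ4 | primary | with a support group | own baseline | Olweus |
| sRQ5–sRQ7 | secondary | with a support group | own baseline | SDQ, KIDSCREEN-27, GSE |

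pRQ4 shares its children, comparator and time point with the secondary block. It shares only its label with the primary block. The statistical analysis section plans to report between-group changes, which pRQ4 cannot yield.

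**2. Can the bias be sized?** If a group's mean at baseline is k standard deviations worse than the population mean, and the measure correlates r with itself over time, the expected shift with no effect is

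shift = (1 − r) × k × SD,

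provided selection acts on follow-up only through the baseline value. For Olweus bullying the protocol gives none of r, k or SD, and no rate of natural recovery. Borrowing the correlation of 0.7 stated for KIDSCREEN gives 0.3 × k × SD. With k assumed anywhere from 0.25 to 1.5, that runs from 0.075 to 0.45 SD. Entry depends on loneliness rather than on the Olweus score, so even this range is only an illustration. The likely direction is known (towards less reported bullying), but the size is not.

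**3. What the sample sizes cover**

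*School level.* Inputs: 10% against 6%, two-sided 5%, 80% power. With a pooled proportion of 0.08,

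n = [1.960 × √(2 × 0.08 × 0.92) + 0.842 × √(0.10 × 0.90 + 0.06 × 0.94)]² / 0.04² = 721 per arm.

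This matches the protocol's 721, so that number belongs to the between-school comparison of proportions.

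*Individual level.* Inputs stated: change of 3 points, correlation 0.7, 5% level. Not stated: SD, power, sidedness. Assuming SD 10, 80% power and a two-sided paired test:

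- SD of change = 10 × √(2 × (1 − 0.7)) = 7.75
- normal approximation: n = [(1.960 + 0.842) × 7.75 / 3]² = 52.3
- paired t-test: n = 55, the protocol's figure

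On the same assumptions, an SD of 8, 9, 12 or 15 gives 36, 45, 78 or 120. So 55 is consistent with a paired test on the KIDSCREEN domain at 9 months.

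*pRQ4.* Its outcome is Olweus bullying and its time point is intervention end. Neither calculation uses that outcome in these children or that contrast. No corrected number can be given, because the protocol states no expected change, spread or rate for bullying in this group.

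**The case against.** The protocol hides nothing. pRQ4 says openly that the comparison is with baseline, and the Study design section says that measurement is confined to intervention schools. Bullying is also named as the main outcome, so ranking it above mental health and self-efficacy within one design is defensible. That explains sRQ5 and sRQ7. It fits sRQ6 less well, since quality of life is itself primary in pRQ2. The difference in labels is therefore supporting evidence, not a contradiction. Disclosure, for its part, does not turn an uncontrolled change into evidence of effectiveness.

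Some stronger readings are tempting, and the documents do not support them:

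- *That pRQ1 already answers pRQ4's question.* It does not. pRQ1 covers all students with the student survey, and the Safety Considerations section describes the all-student questionnaire as anonymous. As described, it cannot single out children with a support group.
- *That the sample size section is wrong, or claims to power pRQ4.* The 55 is consistent with plausible inputs, and the section names its own outcome and time point.
- *That a significant pRQ4 result is likely with no effect.* With 55 children a modest change would reach significance, but that is true of any paired comparison of this size. It says nothing about how much change would occur untreated.
- *That the sentence* "We expect these effects to persist even after 6 and 9 months" *is a causal claim about pRQ4.* It follows two hypotheses, one of them about all children in intervention schools. The wording of sRQ8 is the firmer ground.
- *That intervention end is undefined for these children.* This is a separate matter, which the study flow and timeline figures or the implementation manual may settle. I could not see them.

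**Conclusion.** The point holds as a question of labelling and interpretation. pRQ4 is the only primary question without a control group. Its children enter because of a current adverse state, and no stated calculation supports it as primary. A reduction in bullying under pRQ4 could not be attributed to the support group. The size of the possible bias cannot be derived from the protocol, and none is claimed here.

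The randomised comparisons pRQ1 to pRQ3 are not affected. The conclusion rests on the protocol's own labels, its statement of where individual outcomes are measured, and its description of who receives a support group. It does not depend on the SD or power assumed above to reproduce 55.

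**What to change.** - Relabel pRQ4 as secondary and descriptive, alongside sRQ5 to sRQ7.
- Report it as within-child change with a 95% confidence interval, and make no effectiveness claim from it or from its follow-up in sRQ8. In sRQ8, speak of changes rather than effects for the before-after questions.
- Name natural recovery and regression to the mean as limits of these comparisons.
- Keep pRQ1 to pRQ3 as the primary effectiveness evidence.

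The cost is a protocol amendment; no new data, visits or consent are needed. The real loss is that no primary question would remain specific to the children who receive a support group, and the sponsor should accept that knowingly. If the change is made after the September 2024 start of the intervention, it must be dated and disclosed as a change to the primary questions.

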Bullying is defined as repeated aggressive behaviour characterised by an observed or perceived power imbalance between the victim and perpetrator (Olweus et al., 1983). A newer definition includes social exclusion and points out exclusion as a possibility in all social groups and contexts. The risk of being judged unworthy to belong to a social group includes feelings of being misunderstood, not seen, socially threatened and deprived of dignity (Søndergaard, 2012). Bullying is considered to be a significant public health problem with both short- and long-term physical and social-emotional consequences for the victim (Gaffney et al., 2019). The negative consequences of bullying are pervasive, and bullying exposure in childhood is also associated with poor mental and physical health, lack of social relationships, economic hardship, and decreased quality of life in early adulthood and midlife (Klomek et al., 2015; Koyanagi et al., 2019; Lereya et al., 2015). A good psychosocial environment in school is paramount in reducing the burden associated with mental health disorders in young people (Arango et al., 2018). Hence, the government of Norway have maintained that in accordance with regulation for health promotion and prevention in the school health services, the school nurse and school staff should collaborate to create a good and healthy environment for the children. If there is any indication of bullying, school nurses, in collaboration with school staff, are obliged to intervene early at class-, group- and/or individual level (Norwegian Directorate of Health, 2019). Although appropriate actions and practice to prevent bullying and create a good environment within the schools exist (Eriksen, 2018a; NOU, 2015), bullying is still reported to affect around 14.7 % of children and young people in Nordic countries (Krusell et al., 2019), and six percent of children in Norway (Wendelborg, 2021). The Norwegian student survey for 2023 shows a clear increase in elementary school students experiencing bullying. In the 7th grade, 13 percent responded to being subjected to bullying, while in the 10th grade, the percentage was 11 percent (NOU 2023:1 Regjeringen.no).

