Step 2: Meeting with the participants that are selected to the support group. Create motivation to participate in the group and invite students to come up with suggestions to help the bullied child.
Step 3: Follow up meeting with the bullied/excluded child. In line with SFA, look for progress, create motivation and faith that he/she can contribute to make a change.
Step 4: Follow up meeting with the support group. Give positive feedback and confirm all efforts made. The progress continues until the situation improves.

Process evaluation Quantitative data from the process evaluation will provide information on fidelity, dose, and reach. Qualitative data will inform changes in implementation, experiences of the intervention and unanticipated pathways (table 2). Data will be collected at different timepoints to capture changes to the intervention over time. Process and outcome evaluators will not be completely separated which allows for data on implementation to be integrated into the analysis and interpretation of outcomes. This will also reduce the measurement burden on participants.

Outcome measures: All outcomes will be measured using validated inventories, table 2. The main outcome bullying will be evaluated with the Olweus questionnaire (Olweus., 2013). Quality of life (HRQoL) will be evaluated through the use of the Kidscreen-27 (Haraldstad et al., 2011), a validated 27-item scale.

Table 2 Overview of planned studies, outcome measures and time of measurement.

No	Population	Outcome	Outcome measure	Time of measurement	RQno ^a
Study 1	All students	Bullying Quality of life Class environment	Elevundersøkelsen-UDIR	Baseline, intervention end and after 6- and 9-months	pRQ1-3, sRQ8
Study 2 and 3	Participants with a peer support group	Bullying Quality of life Mental health General self- efficacy	Olweus ^{II} KID screen-27 ^I SDQ ^{III} GSE scale ^{IV}	Baseline, intervention end and after 6- and 9-months	pRQ4, sRQ5-8

Study 4	children, teachers, school nurses and residents	Participant perspectives on study implementation	Quantitative data Qualitative data	At implementation, intervention, intervention end and after 6 months	sRQ9-12
---------	---	--	------------------------------------	--	---------

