
Follow-up of participants

All study support group participants will receive post-study follow-up consultations with the school nurse or social teacher after the intervention. *Adults for Children*'s experience with research involving children and will carefully address the ethical responsibilities, including how to inform children, in their 3-days training program. Participants from *Adults for Children* and the researchers are available for teachers, school nurses, children, and their parents throughout the study. A safety plan is also prepared for additional support should be necessary after the study concludes. If the intervention yields positive effects, all control schools will be invited to implement the intervention as per protocol soon after the conclusion of the study.

Data protection and statistical analysis

We will seek ethical approval for the study from the Regional Ethical Research Committee (REC) in South-East Norway and ensure compliance with data privacy regulations in line with NSD and EUs privacy regulation GDPR. Data will be collected through and stored in the secured server *Tjenester for Sensitive Data* (TSD), integrated solution for collecting and storing sensitive data, managed by the University of Oslo. This includes recording of interview-data through the use of Nettskjema-diktafon in TSD. This is in line with OsloMet's standards for confidentiality and data protection. A risk assessment with appropriate actions will be conducted prior to study implementation.

Baseline data will be presented descriptively. We will use 1600 children (9 schools in each arm) for comparison between intervention- and control schools on school-level. Generalized mixed models (GLM)

for repeated will be used to explore intervention outcomes on individual level for children who were targeted for support groups. GLM will also be used to analyse possible differences on school level. The results will be reported as the estimated between group changes with 95% confidence intervals.

For the process evaluation, descriptive statistical analysis of quantitative data and content analysis of qualitative data will be carried out.

Quality assurance

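### Secondary question sRQ8 sets a pre-intervention baseline comparator for R1-R3, whose 6- and 9-month effects pRQ1-3 define against control schools

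*Protocol*

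**What the plan says.** The protocol sets two kinds of comparator, one for each level of the intervention.

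- **School level, R1-R3.** Under Research questions, pRQ1-3 concern bullying, quality of life and classroom environment in all pupils. Each is "compared to children in control schools receiving usual care, at intervention end and after 6- and 9 months".
- **Support-group children, R4-R7.** pRQ4 asks how far these children "report a reduction in bullying at the end of the intervention compared to their pre-intervention baseline level". sRQ5-7 use the same comparator for mental health, quality of life and self-efficacy, also at intervention end only. Study design explains why no control group exists here: "for this part the outcomes will be measured on individual level in the intervention cluster only".

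sRQ8 then spans both sets: "To what extent does the effects as measured in R1-R7 persist 6- and 9 months after intervention end compared with pre-intervention baseline level".

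Table 2 repeats the overlap. Its Study 1 row, covering all students, reads "Baseline, intervention end and after 6- and 9-months pRQ1-3, sRQ8".

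The only analysis text, under Data protection and statistical analysis, plans the survey data "for comparison between intervention- and control schools on school-level" and says results will be given as estimated changes between groups with 95% confidence intervals.

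**The concern.** For R1-R3 the same outcomes, pupils and follow-up visits carry two comparators: control schools in pRQ1-3 and the pre-intervention period in sRQ8. sRQ8 mentions no control group. An analyst who follows its wording would answer the persistence question for the randomised outcomes from before-after change, which cannot separate an intervention effect from anything else that moves bullying reports over the interval.

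That interval is long. Duration of the project puts delivery from September 2024 to September 2025. If intervention end means the close of that window, the 9-month survey falls around June 2026. Secular trend, season and ageing would all enter a baseline comparison. The protocol's own Background reports from the 2023 student survey a "clear increase in elementary school students experiencing bullying", so a stable background cannot be taken for granted.

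At stake is one secondary conclusion: a statement that the school-level effect did or did not last, which could disagree with the pRQ1-3 result at the same visit.

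**Working it through.** **1. Comparators side by side**

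| Questions | Population | Comparator | Visits |
|---|---|---|---|
| pRQ1-3 | All students, both arms | Control schools | End, 6 and 9 months |
| pRQ4, sRQ5-7 | Support-group children, intervention schools only | Own baseline | End |
| sRQ8 applied to R4-R7 | As the row above | Baseline | 6 and 9 months |
| sRQ8 applied to R1-R3 | All students | Baseline | 6 and 9 months |

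The third row is coherent: it carries R4-R7 to visits that those questions do not cover, with the only comparator available. The last row conflicts with the first. R1-R3 also need no follow-up question, since pRQ1-3 already include 6 and 9 months.

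Study objectives suggests how this arose. The sentence "We expect these effects to persist even after 6 and 9 months" comes directly after the hypothesis about support-group children against their own baseline. The R4-R7 comparator appears to have been extended to R1-R7.

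**2. The plan's own figure**

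Sample size calculation gives 721 children per arm at 5% significance and 80% power. Taking 10% (the top of the anticipated 6-10%) against 6%, two-sided, with pooled variance under the null:

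n = [1.960 × √(2 × 0.08 × 0.92) + 0.842 × √(0.10 × 0.90 + 0.06 × 0.94)]² / 0.04²
= [0.752 + 0.322]² / 0.0016 ≈ 721.

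The figure is reproduced. It shows only that the school-level comparison was sized as a two-arm contrast. The point about the comparator rests on no sample-size figure.

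**3. What a baseline comparator measures**

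Let p₀ be the baseline proportion in both arms, b the background change common to both arms, and e the true reduction due to the intervention.

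- Intervention schools at follow-up: p₀ + b − e
- Control schools at follow-up: p₀ + b
- Fall from baseline in intervention schools: p₀ − (p₀ + b − e) = e − b
- Difference between arms: (p₀ + b) − (p₀ + b − e) = e

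The baseline comparison is off by exactly b, whatever p₀ is. With p₀ = 10%, and e either the planned 4 points (10% − 6%) or zero:

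| e (points) | b (assumed, points) | Control | Intervention | Fall from baseline | Between arms |
|---|---|---|---|---|---|
| 4 | +1 | 11% | 7% | 3 | 4 |
| 4 | +2 | 12% | 8% | 2 | 4 |
| 4 | +3 | 13% | 9% | 1 | 4 |
| 0 | −1 | 9% | 9% | 1 | 0 |
| 0 | −2 | 8% | 8% | 2 | 0 |
| 0 | −4 | 6% | 6% | 4 | 0 |

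Every value of b is an assumption; the protocol gives none for the trial period.

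**4. Chance of a misleading significant result with no effect**

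Take 793 children (the protocol's inflated number per arm) at each of two visits in intervention schools, treated as independent samples without clustering. The probability of a significant fall is

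Φ{[d√n − 1.960 × √(2p̄(1 − p̄))] / √(p₀(1 − p₀) + p₁(1 − p₁))},

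where p₁ is the follow-up proportion, d = p₀ − p₁ and p̄ is the mean of p₀ and p₁. It is about 10% for a drift from 10% to 9%, 29% for 10% to 8%, and 84% for 10% to 6%. A between-arm comparison would keep its nominal error rate. These figures show direction and rough scale only, because clustering is ignored and the drifts are assumed.

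**5. Linkage**

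Safety Considerations describes the all-student questionnaire as anonymous, with no name or personal number. As described, a child's follow-up answers cannot be tied to that child's baseline. For R1-R3, sRQ8 would therefore compare school-level aggregates over time, unlike the within-child change intended for R4-R7.

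**The case against.** The strongest reply is that little is lost. pRQ1-3 are primary, name the control schools, and cover 6 and 9 months. sRQ8 is secondary and nowhere replaces them; a secondary question may have a different reference point. A reader might infer that the trial turns its randomised follow-up contrast into an uncontrolled one. The documents do not support that: the control arm drops out only within sRQ8. This part of the objection stands.

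It also stands that sRQ8 contains no decision rule. It asks to what extent effects persist, with no threshold or test. A reader might infer that the protocol would formally declare an effect lost or maintained on the baseline comparison, but no such criterion is written.

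The background shifts are hypothetical too. It is tempting to take the 13% in the Background as evidence of a 3-point rise over the 10% planning value. That figure is for 7th grade only, whereas 10% is the top of a 6-10% planning range for 5th-7th grade from other sources. The gap mixes grade and source and is not a trend measured over the trial. The falls have no source in the protocol.

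Finally, sRQ8 could be read charitably. It refers to effects as they were measured, which for R1-R3 means against controls, and the analysis section reports changes between groups. On that reading sRQ8 means change from baseline compared across arms. This does not rescue the wording. sRQ8 names the baseline and no control group. If the charitable reading were intended, sRQ8 would duplicate pRQ1-3 for R1-R3 and make one contrast both primary and secondary. Either way the text needs correcting. A statistical analysis plan, not shown here, could add detail, but the comparator is already stated in the protocol.

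**Conclusion.** The point holds as a limited inconsistency. For R1-R3, sRQ8 and the Study 1 row of Table 2 attach a pre-intervention baseline comparator to effects that pRQ1-3 and the planned between-group reporting define against control schools at the same visits. The primary randomised contrast is intact. A persistence statement for R1-R3 made under sRQ8 as worded would be an uncontrolled before-after result, wrong by the full amount of any background change.

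The size cannot be fixed from the protocol. Under assumed shifts and equal baselines in the arms, a fully persistent 4-point effect would show as 3 to 1 points if the background rose by 1 to 3 points. No effect would show as a 1- to 4-point reduction if the background fell by 1 to 4 points. For R4-R7 the baseline comparator agrees with the design as described. The correction is worth making because it is nearly free and removes a conflict in how the follow-up results are reported.

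**What to change.** 1. Limit the baseline comparator in sRQ8 to R4-R7, the outcomes measured in intervention schools only.
2. State that persistence for R1-R3 is the intervention-versus-control difference at 6 and 9 months, as pRQ1-3 already define it.
3. In the Study 1 row of Table 2, remove sRQ8, or keep it only if sRQ8 is reworded as that between-arm contrast.

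If change from baseline in the all-student survey is still of interest, present it descriptively for both arms side by side and draw no conclusion on persistence from the intervention arm alone.

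The cost is one sentence and one table cell. Data collection, sample size, the primary questions and the planned model stay as they are.
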